2.1. Eligibility Criteria

2.1.1. Inclusion Criteria

- a. Histologically or cytologically confirmed gastric adenocarcinoma
 - b. Metastatic disease must be measurable by CT and/or MRI
 - or*
 - There must be a history of positive peritoneal washings or carcinomatosis
 - c. All disease should be deemed resectable to negative margins (NED) based on imaging studies e.g.:
 - Esophageal invasion <4cm that does not require thoracotomy (Seiwert II and III lesions)
 - Hepatic metastases (unilateral or bilateral ≤ 5 lesions, ≤ 15 cm total diameter)
 - Primary peritoneal metastases (small disease load \leq P2 disease) without massive ascites or intestinal obstruction
 - Para-aortic lymph node metastases (stations 16 a1 and/or b2, see appendix 5)
 - Lung metastases (≤ 3 unilateral/bilateral, 9 cm total diameter)
 - Patients who present with both hepatic and peritoneal metastases must have no evidence of extensive para-aortic/retro-pancreatic lymph node metastases
- Note:** Patients with both pulmonary and peritoneal metastases will be enrolled at the discretion of the PI
- d. Greater than or equal to 18 years of age
 - e. Must be able to understand and sign the Informed Consent Document
 - f. Clinical performance status of ECOG ≤ 2
 - g. Life expectancy of greater than three months
 - h. Patients of both genders must be willing to practice birth control during and for four months after receiving chemotherapy
 - i. Hematology:
 - Absolute neutrophil count greater than $1500/\text{mm}^3$ without the support of Filgrastim.
 - Platelet count greater than $75,000/\text{mm}^3$.
 - Hemoglobin greater than 8.0 g/dl.
 - j. Chemistry:
 - Serum ALT/AST less or equal to 5 times the upper limit of normal; except in the presence of obstructive liver metastases where ALT/AST may be up to 10 times the upper limit of normal
 - Serum creatinine less than or equal to 1.5 mg/dl unless the measured creatinine clearance is greater than $60 \text{ mL/min}/1.73 \text{ m}^2$
 - Total bilirubin less than or equal to 2 mg/dl, except in the presence of obstructive metastases
 - PT within 2 seconds of the upper limit of normal (INR ≤ 1.8)
 - k. No history of prior/other malignancies within the 2 years prior to enrollment with the exception of basal cell carcinoma

2.1.2.

Exclusion Criteria

- a. Prior treatment with FOLFOXIRI (treatment with any of the components as separate regimens is allowable)

- b. Inability to tolerate any of the chemotherapeutic agents
- c. Grade 2 or greater neuropathy
- d. Women of child-bearing potential who are pregnant or breastfeeding because of the potentially dangerous effects of the chemotherapy on the fetus or infant.
- e. Active systemic infections, coagulation disorders or other major medical illnesses of the cardiovascular, respiratory or immune system, myocardial infarction, cardiac arrhythmias, obstructive or restrictive pulmonary disease.
- f. Brain metastases or a history of brain metastases
- g. Childs B or C cirrhosis or with evidence of severe portal hypertension by history, endoscopy, or radiologic studies
- h. Weight less than 40 kg
- i. Significant ascites, greater than 1000cc in the absence of peritoneal disease
- j. History of congestive heart failure and/or an LVEF < 40%
Note: Patients at increased risk for coronary artery disease or cardiac dysfunction (e.g., >65yo, diabetes, history of hypertension, elevated LDL, first degree relative with coronary artery disease) will undergo full cardiac evaluation and will not be eligible if they demonstrate significant irreversible ischemia on stress thallium or an ejection fraction <40%.
- k. Significant COPD or other chronic pulmonary restrictive disease with PFT's indicating an FEV1 less than 50% or a DLCO less than 40% predicted for age
Note: Patients who have shortness of breath with minimal exertion or who are at risk for pulmonary disease (e.g., chronic smokers) will undergo pulmonary function testing and will not be eligible if their FEV1 is < 50% of expected.
- l. Concomitant medical problems that would place the patient at an unacceptable risk for a major surgical procedure or for the administration of FOLFOXIRI

2.2. Research Eligibility Evaluation

2.2.1. Within 6 weeks prior to treatment:

- Complete physical examination including vital signs, height and weight as well as ECOG assessment.
- HIV, Hepatitis B surface antigen and Hepatitis C antibody
- UGT1A1genotyping (selected patients)
- 12 lead EKG
- Patients will undergo pulmonary function tests as indicated in section 2.1.2 i.
- Cardiac evaluation with possible stress test for patients with history of cardiac disease will be performed as indicated in section 2.1.2h
- Thoracic oncology consult for patients with pulmonary metastases
- Pathology will be confirmed by the NCI Laboratory of Pathology.

- Radionuclide bone scan, when clinically indicated.
- MRI Brain when indicated.
- PET-CT when indicated.
- EGD-EUS when indicated.
- Female patients will undergo pelvic ultrasound and/or MRI if indicated.

2.2.2. Within 4 weeks prior to treatment:

- Baseline imaging: CT scan of chest, abdomen and pelvis (CT C/A/P) with triphasic 1mm cuts as per the liver scan protocol. For patients with evidence of hepatic disease, a baseline MRI-L will be performed. Note: If the screening CT and MRI of the liver are consistent indicating that CT is an accurate reflection of hepatic disease, then CT may be used for baseline and subsequent evaluations.
- Randomization (**Note:** patients should begin treatment as soon as feasible following randomization)
- *Helicobacter pylori* IgG Antibody
- Patients who test positive for *H. pylori* will receive:
 - Omeprazole 20 mg po daily x 10 days
 - Clarithromycin 500 mg po twice daily x 10 days
 - Amoxicillin 1000mg po twice daily x 10 days

OR

 - Omeprazole 20 mg po daily x 10 days
 - Clarithromycin 500 mg po twice daily x 10 days
 - Metronidazole 500 mg po twice daily x 10 days

2.2.3. Within 3 – 6 weeks prior to treatment (one week prior to randomization):

All patients will have a definitive staging laparoscopy and peritoneal washings. Pathology results of peritoneal washings must be completed before randomization. (**Note:** patient should be randomized as soon as feasible following laparoscopy)

2.2.4. Within 2 weeks prior to treatment:

- Laboratory evaluation
 - CBC with platelets
 - Chem-20 (Sodium (Na), Potassium (K), Chloride (Cl), total CO₂ (bicarbonate), Creatinine, Glucose, Urea nitrogen (BUN), Albumin, Calcium total, Magnesium total (Mg), Inorganic Phosphorus, Alkaline Phosphatase, ALT/GPT, AST/GOT, Total Bilirubin, Direct Bilirubin, LD, Total Protein, total CK, Uric acid
 - Ferritin, Prealbumin,
 - PT/PTT & INR,
 - Urinalysis
 - iron levels, B12 levels, c-reactive-protein
 - tumor markers (CEA, CA19-9, AFP, CRP, CA 15-3, CA 27-29 and CA125)

- Anesthesia consult – for patients randomized to the surgery arm

2.2.5. Within 2-3 days prior to chemotherapy

- Complete physical examination including vital sign measurements, weight and ECOG assessment should be conducted within 3 days prior to treatment. This can be performed by home oncologist if patient decides to undergo systemic therapy at home.
- Serum beta-HCG on all females of child bearing potential or urine pregnancy test within 2 days prior to treatment.

2.2.6. On Study within 1 week of surgical treatment:

- Physical examination including vital sign measurements, weight and ECOG assessment.
- Laboratory evaluation: CBC, platelets, Chem-20 (Sodium (Na), Potassium (K), Chloride (Cl), total CO₂ (bicarbonate), Creatinine, Glucose, Urea nitrogen (BUN), Albumin, Calcium total, Magnesium total (Mg), Inorganic Phosphorus, Alkaline Phosphatase, ALT/GPT, AST/GOT, Total Bilirubin, Direct Bilirubin, LD, Total Protein, total CK, Uric acid, PT/PTT & INR, Urinalysis.
- Base line tumor markers, Prealbumin and Ferritin.

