2.3. Patient Registration, Stratification, and Randomization

Registration of patients onto this study will take place within 10 days of the patient signing the consent by faxing a completed eligibility checklist to the Central Registration Office (CRO) at [contact] between 9:00 and 5:00 Monday through Friday. Following laparoscopy, patients will be stratified and then randomized by the CRO to receive gastrectomy and/or metastasectomy plus systemic therapy (GYMS arm) or standard therapy (SA arm). The CRO will notify the Study Coordinator of the results of randomization.

Note: As soon as the patient has signed the informed consent, the patient's referring oncologist (or [name] or his designee for those patients being treated at the NCI) will be notified of the expected date of randomization and potential start dates for the chemotherapy. Immediately following randomization the referring oncologist will be notified. Subjects who are randomized to receive chemotherapy only must begin chemotherapy treatment within 14 days following randomization.

Stratification will be done according to the following factors:

- Site of metastases (liver, lung, and peritoneal disease). Note: positive peritoneal washings will be stratified as peritoneal disease.
- Time to development of first metastases (earlier than 1 year vs. later than 1 year)
- Previous systemic therapy specifically given for gastric metastases vs. no therapy for metastatic disease. (**Note:** patients who have received adjuvant chemotherapy will be stratified to the *no therapy for metastatic disease* group)

3. Study Implementation:

Study Design (See appendix 3 for trial schema)

Experimental Design:

- This is a prospective randomized trial comparing the effects of two therapeutic approaches, gastrectomy and/or metastasectomy plus systemic therapy (GYMS) to systemic therapy alone (SA) on the overall survival of patients with limited gastric cancer metastases.
- Patients who are newly diagnosed as well as those who have received prior systemic treatment for gastric metastases will be eligible. Both groups will be randomized to surgery plus chemotherapy or chemotherapy alone.
- Candidate patients for this trial will undergo all or part of the following staging elements before randomization and/or if indicated medically: pathologic confirmation of gastric cancer as feasible, H&P, laboratory evaluations, imaging studies and other studies as medically indicated.

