- Patients who enroll and are willing to have tissue collected for research purposes will be enrolled on protocol 09-C-0079.
- All patients found eligible will undergo staging laparoscopy with peritoneal lavage prior to randomization.
- Patients will be randomized following staging laparoscopy and after the results of the peritoneal washings are available.
- Stratification will adjust for site of metastases (liver, peritoneal and lung), disease-free interval (DFI), and previous systemic therapy for gastric metastases. Note: positive peritoneal washings will be stratified as peritoneal disease.
- Patients randomized to the GYMS approach and who have peritoneal disease will undergo, as an integral part of their treatment, complete peritonectomy and peritoneal perfusion (CHPP).
- Patients who present with intrabdominal disease without peritoneal involvement will undergo CHPP with limited peritonectomy as described in section 3.2.6
- All patients randomized to the GYMS arm will undergo gastrectomy, modified D2 lymph node dissection and/or appropriate metastasectomy followed by systemic therapy.
- *H. pylori* infection will be tested and treated following the recommendations of the American College of Gastroenterology guideline on the management of *H. pylori* infection⁷⁵ (Appendix 2). This treatment should not delay surgery.
- Patients randomized to the systemic therapy arm (SA) will receive systemic therapy preferably by their home medical oncologist or by the NCI Medical Oncology Branch.
- Systemic therapy: Since there is no definitive standard of care in metastatic gastric cancer and oxaliplatin and/or irinotecan were shown in phase III trials⁷⁶ to be equally effective to other common regimens in gastric cancer, patients will receive the FOLFOXIRI regimen as described by Masi et al from the GONO group⁷⁷.
- Patients in the SA arm who develop metastases synchronous to the primary gastric cancer will be eligible for palliative gastrectomy for pain, bleeding, obstruction and/or if deemed in the best interests of the patients.
- Palliative gastrectomy will include tumor resection (R0 when possible) and a bypass. As per standard of care, no adjacent organ resection (with the exception of obstructing lesions) will be performed.

- During follow up, all patients will undergo H&P laboratory evaluation and imaging studies and tumor markers as indicated. The timing of all follow up evaluations will be based on the date of randomization.

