3.1. Staging Laparoscopy

3.1.1. Patients who meet eligibility criteria will be taken to the operating room for staging laparoscopy and peritoneal washings. At laparoscopy biopsies of the peritoneum will be done and used later to confirm status of peritoneal disease (not as a part of the staging procedure but as part of the study).

- Any suspicious lesions that might preclude resection to NED will be biopsied as well.
- Liver ultrasound to confirm axial imaging findings will be done.
- Randomization and stratification will be done after laparoscopy and only after the results of the peritoneal washings are known (within one week of laparoscopy).

3.1.2. Patients will then be randomized to receive gastrectomy and/or metastasectomy plus systemic therapy (GYMS arm) or systemic therapy alone (SA arm).

- Patients randomized to receive the standard of care (SA arm) will receive systemic therapy (as described in Section 3.5). **Note:** Patients may undergo palliative gastrectomy if indicated but must begin chemotherapy within 6 weeks of gastrectomy (8 weeks following randomization).
- Patients randomized to receive gastrectomy and/or metastasectomy plus systemic therapy (GYMS arm) will be taken to the operating room within 1-2 weeks of randomization (as soon as feasible). Patients may undergo surgery only at the NCI. Subsequently, patients will receive systemic therapy within 4 to 16 weeks after surgery and/or when fully recovered from surgery. Patients who do not recover within 16 weeks will be taken off treatment and followed for survival. (**Note:** patients who undergo thoracotomy for pulmonary metastases must be able to receive systemic therapy within 24 weeks of their initial surgery.) This is an intent-to-treat phase III trial.

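### The only scheduled pregnancy test is tied to the start of chemotherapy: none is required before laparoscopy or randomisation, and in GYMS it can fall weeks after surgery and CHPP

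*Combined protocol and SAP*

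**What the plan says.** Section 2.1.2 d excludes "Women of child-bearing potential who are pregnant or breastfeeding because of the potentially dangerous effects of the chemotherapy on the fetus or infant".

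The one pregnancy test in the schedule is in Section 2.2.5, whose heading places it two to three days before chemotherapy: "Serum beta-HCG on all females of child bearing potential or urine pregnancy test within 2 days prior to treatment".

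The other lists in Section 2.2 name no pregnancy test:

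- Sections 2.2.1, 2.2.2 and 2.2.4 set out the evaluations due within 6, 4 and 2 weeks of treatment.
- Section 2.2.3 covers laparoscopy: "All patients will have a definitive staging laparoscopy and peritoneal washings". This comes before randomisation.
- The pre-surgery work-up has its own heading, "2.2.6. On Study within 1 week of surgical treatment". Its laboratory list is itemised and ends with "total CK, Uric acid, PT/PTT & INR, Urinalysis".

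CHPP is not confined to peritoneal disease. Section 3 (Experimental Design) gives it to GYMS patients with peritoneal disease and adds: "Patients who present with intrabdominal disease without peritoneal involvement will undergo CHPP with limited peritonectomy as described in section 3.2.6".

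**The concern.** The exclusion protects a fetus from cytotoxic drugs, so the test that supports it should come before the first such drug on study. The schedule does not ensure this. In GYMS the first cytotoxic exposure on study is the IV 5-FU and intraperitoneal oxaliplatin given at the operation, whereas the test is attached to the later start of systemic chemotherapy. Women in either arm also have laparoscopy under this schedule with no test required, and an SA patient who needs palliative gastrectomy has that operation before her test.

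At stake is an undetected pregnancy carried through major surgery and chemotherapy perfusion. A positive result after randomisation would also reveal an ineligible patient who already belongs to the intention-to-treat set.

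**Working it through.** The plan gives no figure to reproduce. The check has two parts: which chemotherapy Section 2.2.5 refers to, and where the test then falls.

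**Which chemotherapy**

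Three passages point to systemic chemotherapy:

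- The neighbouring bullet in 2.2.5 lets a home oncologist do the examination for patients having systemic therapy at home. Section 3.1.2 allows surgery only at the NCI.
- Section 2.2.6 treats surgery separately.
- Section 3.5.1 requires eligibility to be met again before chemotherapy begins, in a paragraph where GYMS chemotherapy follows surgery.

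Two points support including CHPP: the bullet itself says treatment, and the title of Section 3.3 calls CHPP intraperitoneal chemotherapy.

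**Inputs**

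- Laparoscopy: within one week before randomisation (3.1.1); 2.2.3 also gives 3 to 6 weeks before treatment.
- GYMS surgery: 1 to 2 weeks after randomisation (3.1.2).
- GYMS systemic chemotherapy: 4 to 16 weeks after surgery (3.1.2), or about 6 to 8 weeks (3.5.1).
- GYMS with thoracic surgery: up to 24 weeks, counted from the initial surgery in 3.1.2 and from randomisation in 3.2.8.
- SA chemotherapy: within 14 days of randomisation (2.3), or by 8 weeks after randomisation if palliative gastrectomy is done (3.1.2).
- Test: up to 2 days before treatment (2.2.5).

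**Systemic-chemotherapy reading, GYMS**

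Test day after surgery = 7 × (weeks from surgery to chemotherapy), less up to 2 days. Chemotherapy start after randomisation = weeks to surgery + weeks from surgery to chemotherapy.

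| Source | Test, days after surgery | Chemotherapy start, weeks after randomisation |
|---|---|---|
| 3.1.2, 4–16 weeks | 28 − 2 = 26 to 112 | 1 + 4 = 5 to 2 + 16 = 18 |
| 3.5.1, 6–8 weeks | 42 − 2 = 40 to 56 | 1 + 6 = 7 to 2 + 8 = 10 |
| Thoracic limit, 24 weeks from surgery (3.1.2) | 168 − 2 = 166 to 168 | up to 2 + 24 = 26 |
| Thoracic limit, 24 weeks from randomisation (3.2.8) | – | up to 24 |

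For the first row, the test falls from day 7 + 26 = 33 to day 14 + 112 = 126 after randomisation.

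CHPP patients have by then received intraperitoneal oxaliplatin 460 mg/m² and IV 5-FU 400 mg/m² (3.3.2).

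**SA**

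The test falls by day 14 after randomisation. After palliative gastrectomy it falls by week 8, and after the operation.

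**CHPP-included reading, GYMS**

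- After randomisation: surgery on day 7 to 14, less up to 2 days, gives day 5 to 14.
- After laparoscopy: up to 7 + 14 = 21 days, or up to 6 × 7 = 42 days if the upper limit in 2.2.3 is used.

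On either reading the test comes after laparoscopy and randomisation.

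**The case against.** The strongest reply is that eligibility already controls entry. Pregnancy is an exclusion, an eligibility checklist is faxed for registration (2.3), and Sections 3 and 3.1.1 send only eligible patients to laparoscopy. A woman known to be pregnant should therefore not reach the operating room. This is right, and it narrows the concern to undetected pregnancy. None of these steps names a test, however, so status at entry could rest on the patient's own report.

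The second reply is that treatment elsewhere in Section 2.2 includes surgery: 2.2.4 lists an anesthesia consult for the surgery arm under its pre-treatment heading. The home-oncologist sentence is also permissive and belongs to the examination bullet, not to the test. If 2.2.5 covers CHPP, the claim of drug exposure before the test falls away. That reading is possible but less natural, and it leaves laparoscopy and randomisation ahead of the test.

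Third, the exclusion is aimed at chemotherapy, not surgery. Operative risk is left to criterion 2.1.2 l and to standard preoperative care (3.2.1), which may in practice include a test. That may be so, but 3.2.1 lists no such test and Section 3.2 keeps perioperative detail off the case report forms. The required willingness to use birth control (2.1.1 h) does not detect a pregnancy already present.

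Finally, few women may be affected. That cannot be settled from the documents, because they give no number of women of child-bearing potential.

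**Conclusion.** The concern holds. There is one scheduled test, it is attached to chemotherapy, and none is required before laparoscopy or randomisation. On the natural reading a GYMS woman is tested about 4 to 16 weeks after resection, and after CHPP where it is given, with up to 24 weeks where thoracic surgery is needed. That timing defeats the purpose of the exclusion, so this is more than a missing detail and should be fixed.

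The intervals after surgery assume that 2.2.5 means systemic chemotherapy. The finding about laparoscopy and randomisation does not depend on that. The drug exposure applies only to patients given CHPP, and lung-only patients are not clearly assigned it. The trial schema (Appendix 3) is a figure not available here and could not be checked. No effect is claimed on the intention-to-treat analysis or on the design figures of 136 patients, 121 deaths and 80% power.

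**What to change.** 1. In the eligibility evaluation, require a negative serum or urine pregnancy test for women of child-bearing potential before laparoscopy and randomisation.
2. In Section 2.2.6, add the same test within 2 days before surgery or CHPP.
3. Keep the test in Section 2.2.5 and reword the heading so that it refers to systemic chemotherapy.

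This takes one line in each of two lists and one change of heading. Each woman of child-bearing potential has one or two additional routine blood or urine tests. No statistical section needs to change.

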2.3. Patient Registration, Stratification, and Randomization

Registration of patients onto this study will take place within 10 days of the patient signing the consent by faxing a completed eligibility checklist to the Central Registration Office (CRO) at [contact] between 9:00 and 5:00 Monday through Friday. Following laparoscopy, patients will be stratified and then randomized by the CRO to receive gastrectomy and/or metastasectomy plus systemic therapy (GYMS arm) or standard therapy (SA arm). The CRO will notify the Study Coordinator of the results of randomization.

Note: As soon as the patient has signed the informed consent, the patient's referring oncologist (or [name] or his designee for those patients being treated at the NCI) will be notified of the expected date of randomization and potential start dates for the chemotherapy. Immediately following randomization the referring oncologist will be notified. Subjects who are randomized to receive chemotherapy only must begin chemotherapy treatment within 14 days following randomization.

Stratification will be done according to the following factors:

- Site of metastases (liver, lung, and peritoneal disease). Note: positive peritoneal washings will be stratified as peritoneal disease.
- Time to development of first metastases (earlier than 1 year vs. later than 1 year)
- Previous systemic therapy specifically given for gastric metastases vs. no therapy for metastatic disease. (**Note:** patients who have received adjuvant chemotherapy will be stratified to the *no therapy for metastatic disease* group)

3. Study Implementation:

Study Design (See appendix 3 for trial schema)

Experimental Design:

- This is a prospective randomized trial comparing the effects of two therapeutic approaches, gastrectomy and/or metastasectomy plus systemic therapy (GYMS) to systemic therapy alone (SA) on the overall survival of patients with limited gastric cancer metastases.
- Patients who are newly diagnosed as well as those who have received prior systemic treatment for gastric metastases will be eligible. Both groups will be randomized to surgery plus chemotherapy or chemotherapy alone.
- Candidate patients for this trial will undergo all or part of the following staging elements before randomization and/or if indicated medically: pathologic confirmation of gastric cancer as feasible, H&P, laboratory evaluations, imaging studies and other studies as medically indicated.
- Patients who enroll and are willing to have tissue collected for research purposes will be enrolled on protocol 09-C-0079.
- All patients found eligible will undergo staging laparoscopy with peritoneal lavage prior to randomization.
- Patients will be randomized following staging laparoscopy and after the results of the peritoneal washings are available.
- Stratification will adjust for site of metastases (liver, peritoneal and lung), disease-free interval (DFI), and previous systemic therapy for gastric metastases. Note: positive peritoneal washings will be stratified as peritoneal disease.
- Patients randomized to the GYMS approach and who have peritoneal disease will undergo, as an integral part of their treatment, complete peritonectomy and peritoneal perfusion (CHPP).
- Patients who present with intrabdominal disease without peritoneal involvement will undergo CHPP with limited peritonectomy as described in section 3.2.6
- All patients randomized to the GYMS arm will undergo gastrectomy, modified D2 lymph node dissection and/or appropriate metastasectomy followed by systemic therapy.
- *H. pylori* infection will be tested and treated following the recommendations of the American College of Gastroenterology guideline on the management of *H. pylori* infection⁷⁵ (Appendix 2). This treatment should not delay surgery.
- Patients randomized to the systemic therapy arm (SA) will receive systemic therapy preferably by their home medical oncologist or by the NCI Medical Oncology Branch.
- Systemic therapy: Since there is no definitive standard of care in metastatic gastric cancer and oxaliplatin and/or irinotecan were shown in phase III trials⁷⁶ to be equally effective to other common regimens in gastric cancer, patients will receive the FOLFOXIRI regimen as described by Masi et al from the GONO group⁷⁷.
- Patients in the SA arm who develop metastases synchronous to the primary gastric cancer will be eligible for palliative gastrectomy for pain, bleeding, obstruction and/or if deemed in the best interests of the patients.
- Palliative gastrectomy will include tumor resection (R0 when possible) and a bypass. As per standard of care, no adjacent organ resection (with the exception of obstructing lesions) will be performed.

- During follow up, all patients will undergo H&P laboratory evaluation and imaging studies and tumor markers as indicated. The timing of all follow up evaluations will be based on the date of randomization.
- Progression will be measured by a radiologist blinded as to the treatment arm.

